10.3. Obligations of the Sponsor

During the course of study, the Sponsor will report all SAEs that are both unexpected and considered related to Investigational device to the regulatory authorities and/or IRBs as appropriate and to the Investigators. The Sponsor will report all SAEs that are expected and considered related to the investigational device to the regulatory authorities, according to the local regulations. The Sponsor will report all safety observations made during the conduct of the study in the clinical study report.

10.4. Adverse Events Monitoring

All events will be managed promptly and reported in compliance with all applicable regulations and guidelines, and will be included in the final clinical study report.

10.5. Unscheduled Visits

Patients may contact delegated study staff about possible changes in their health that are more than minor and/or that persist; or delegated study staff may contact patients when additional assessments are deemed needed. Patients may be asked to return to the clinic to repeat laboratory tests or for additional assessment if requested by the Investigator. In these cases, such evaluations/testing will be performed in accordance with those applicable regulations.

11. STATISTICAL EVALUATION

11.1. Sample Size

The sample size calculation was conducted using the software package G*Power (v3.1.9.7) on a two-group independent proportions Fisher's exact-test (one-tailed), chosen as the statistical test for the primary endpoint of this study. A type I (α) error probability of 0.05, and a power (1 – β) of probability 0.85 was chosen for the calculation; an allocation ratio of 1:1 was set to address the equally-sized treatment arms.

According to literature, patient populations that used C&S testing for cUTI management has a favorable clinical outcomes (FCl)percentage ranging from 60%-90% 8. For the purpose of this study, we assumed an FCl percentage of 75% for the C&S arm. A 10% expected improvement of the FCl in the PCR arm will require 574 enrolled participants. Assuming a 25% attrition rate & post-hoc exclusion rate (due to PCR or C&S negative result after randomization), up to 146 additional participants will be enrolled. Thus, up to 720 participants will be sufficient for

UPH-STD-05-01 Version: 0

Effective Date: 06/23/2023 Page **27** of **44**

Doc Lab Inc. / Protocol Number 22-UPHUV-01

Advarra IRB Approved Version 0, Date: 12 May 2023 / Pro00071764

completion of the study. The participants will be enrolled in at least 6 study sites (with an equal distribution of participants enrolled per site).

Exact - Proportions: Inequality, two independent groups (Fisher's exact test)

Options: Exact distribution

Analysis: A priori: Compute required sample size Input: Tail(s) = One Proportion p1 = 0.7 Proportion p2 = 0.8 α err prob = 0.05 Power (1- β err prob) = 0.85

Allocation ratio N2/N1 = 1

Output: Sample size group 1 = 287

Sample size group 2 = 287 Total sample size = 574

Actual power = 0.8513193Actual α = 0.0404397

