7. STUDY TREATMENTS

7.1. Subject Enrollment

Each site will recruit and screen approximately 168 adults to identify the defined study population (n=120) based on an assumed 40% screen failure rate.

Patients will have their eligibility assessed by the Investigator and/or delegate, through the review of relevant medical history and other assessments as defined in the protocol.

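### The sample-size figures do not follow from their stated assumptions: 574 belongs to 70% vs 80%, 720 does not cover a 25% loss, and 168 screened per site does not yield 120

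*Combined protocol and SAP*

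**What the plan says.** Section 11.1 plans a "two-group independent proportions Fisher's exact-test (one-tailed), chosen as the statistical test for the primary endpoint". It adds: "A type I (α) error probability of 0.05, and a power (1 – β) of probability 0.85 was chosen for the calculation", and "an allocation ratio of 1:1 was set to address the equally-sized treatment arms". The narrative takes "an FCl percentage of 75% for the C&S arm. A 10% expected improvement of the FCl in the PCR arm will require 574" participants. The G*Power printout that closes the same section lists "Proportion p1 = 0.7 Proportion p2 = 0.8" as its inputs and returns 287 per group, 574 in total, with actual power 0.8513193 and actual alpha 0.0404397.

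The section then assumes a 25% rate of attrition and post-randomization exclusion for negative test results. For this it says "up to 146 additional participants will be enrolled", which brings the ceiling to 720.

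Section 7.1 states: "Each site will recruit and screen approximately 168 adults to identify the defined study population (n=120) based on an assumed 40% screen failure rate".

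Section 11.3.1 makes the Mod-ITT population the primary analysis set. Section 11.2 defines that set so as to leave out randomized patients without a positive result.

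**The concern.** Three links in the chain from assumption to headcount look broken.

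- The proportions in the text and in the printout differ, so it is unclear which effect the trial was designed to detect. The text also does not say whether the 10% is in percentage points or relative to 75%.
- The loss allowance appears to have been added as a percentage of the evaluable target, although a loss is a percentage of those enrolled.
- The screening figure appears to make the same mistake.

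At stake is the plan's only power statement, 0.85 at 574. If these readings are right, it describes neither the stated assumptions nor the number of patients expected in the primary analysis. Section 5.4 plans no interim analysis, so no scheduled look would bring the mismatch to light before the end.

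**Working it through.** **Inputs.** From section 11.1: one-tailed Fisher's exact test, alpha 0.05, target power 0.85, 1:1 allocation, C&S rate 75% with a 10% gain (text), 0.70 and 0.80 (printout), 25% loss, 146 added, 720 in total. From section 7.1: 168 screened, 120 enrolled, 40% screen failure.

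**Method.** For n per arm, enumerate all pairs of binomial outcomes, mark those where the one-sided hypergeometric tail probability is at most 0.05, and sum their probabilities under the assumed rates.

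**Step 1: reproduce 574.**

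- 70% vs 80%, 287 per arm: power 0.8513193, as printed.
- 70% vs 80%, 286 per arm: power 0.84997, just under target, so 287 is the smallest size reached.
- Both rates 80%, 287 per arm: rejection probability 0.0404397, matching the printed actual alpha.

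The 574 is therefore the correct answer for 70% vs 80%.

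**Step 2: apply the stated 75%.**

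| Rates (C&S vs PCR) | Per arm for 0.85 | Total | Power at 287 per arm |
|---|---|---|---|
| 70% vs 80% (printout) | 287 | 574 | 0.851 |
| 75% vs 85% (10 points absolute) | 246 | 492 | 0.898 |
| 75% vs 82.5% (75% × 1.10, relative) | 452 | 904 | 0.677 |

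Neither reading of the text gives 574.

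**Step 3: the 25% loss.**

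- What was done: 574 × 1.25 = 717.5, evidently raised to 720 (574 + 146).
- What a 25% loss requires: 574 / 0.75 = 765.3, so 766 enrolled.
- What 720 delivers: 720 × 0.75 = 540 evaluable, 270 per arm, and 574 − 540 = 34 short.
- Loss that 720 can absorb while keeping 574: 146 / 720 = 20.3%.

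Power at 270 per arm is 0.830 for 70% vs 80%, 0.880 for 75% vs 85%, and 0.651 for 75% vs 82.5%.

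**Step 4: screening.**

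- What was done: 120 × 1.4 = 168.
- What 168 yields at 40% failure: 168 × 0.60 = 100.8, about 101 per site.
- What 120 requires: 120 / 0.60 = 200 per site.
- Failure rate implied by 168 screened and 120 enrolled: 1 − 120/168 = 28.6%.

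**Step 5: the compounded case (hypothetical).** Suppose exactly six sites stopped screening at 168 each. Then 6 × 168 = 1,008 screened, × 0.60 ≈ 605 enrolled, × 0.75 ≈ 454 evaluable, or 227 per arm. Power would be 0.76 for 70% vs 80% and 0.82 for 75% vs 85%.

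**The case against.** The arithmetic is not in dispute. The case against concerns how much it matters, and much of it stands as a limit on the consequence.

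- **On the most natural reading there is no shortfall.** If the intended contrast is 75% vs 85%, only 492 evaluable are needed. The 540 left after the full 25% loss give 0.88, so the mismatch errs on the safe side. Under 70% vs 80% the gap is about two points of power. This stands.
- **The relative reading is weakly supported.** The printout uses a gap of 0.10 in absolute terms, which points to percentage points. This stands. The 904 and the powers of 0.68 and 0.65 show why the word absolute is needed; they do not describe the likely design.
- **Screening follows enrollment.** The 168 is given as approximate, nothing caps screening, and at least six sites are planned. If sites screen until 120 are enrolled, the error affects recruitment planning and not power. This stands, and step 5 applies only if screening stops at 168 at exactly six sites.
- **540 is an assumption.** The Mod-ITT definition does not itself remove patients lost to follow-up, so more than 540 might be analyzed. That is possible, but the plan itself budgets the whole 25% as loss, and 540 follows from that budget.
- **Section 5.3.2 ties the last enrollment to reaching an adequate number of qualifying subjects.** That does not repair the figure, because section 11.1 sets 720 as the upper limit.

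**Conclusion.** The point holds in all three parts, and the figures are wrong as written. The 574 comes from 70% vs 80% and does not follow from 75% plus 10% on either reading. With the plan's own 25% loss, 720 enrolled leave 540 evaluable, so the stated power of 0.85 becomes 0.83 on the printout's rates or 0.88 for 75% vs 85%. The 168 screened per site yield about 101 enrolled.

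This should be corrected, but it does not undermine the trial's size if 75% vs 85% is what was meant. The power figures assume the stated one-sided test at 0.05, equal arms, and the full 25% loss falling equally on both arms. The screening shortfall reduces power only if screening actually stops at 168.

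**What to change.** 1. In section 11.1, put the same pair of proportions in the text and in the G*Power box, and state that the 10% is an absolute difference.
2. Restate power for the evaluable number that 720 delivers under a 25% loss, 540 (270 per arm): 83% for 70% vs 80%, or 88% for 75% vs 85%. If the sponsor prefers to keep 574 evaluable, the enrollment figure has to be 766.
3. In section 7.1, change the number screened to about 200 per site, which is 1,200 over six sites.

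The cost is a recalculation and some wording. Enrollment does not rise if power is restated; only the planned number to screen does.

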11.2. Study Population

The Intention-to-Treat (ITT) population: All participants who participate in the study and get randomized into one of the study's arm, without any major protocol violations which would significantly compromise the integrity of collected data.

The Modified Intent-To-Treat (Mod-ITT) Population: All participants from the ITT with a positive PCR or C&S results after randomization assignment.

11.3. Analysis Plan

11.3.1. Analysis Population

The Mod-ITT Population will be used for the analysis of the primary and secondary endpoints (exception for the discordance study, where the ITT population will be used for assessing the agreement between methods).

11.3.2. Primary and Secondary Endpoints

The primary endpoint is the number (and percentage) of patients in each study arm with FCl at the EOS visit; this term is defined as a *clinical response of improvement* and/or *clinical cure*:

Clinical response of improvement is defined as:

1) Resolution of cUTI signs and symptoms present at baseline, and/or

UPH-STD-05-01 Version: 0

Effective Date: 06/23/2023 Page **28** of **44**

- 2) Development of no new cUTI symptoms, and/or
- 3) Avoidance of parenteral antibiotic therapy, in or out of hospital, at any time after randomization

Clinical cure is the resolution of all acute signs and symptoms of cUTI and improvement to such an extent that no further antimicrobial therapy (IV or oral) is required for the treatment of the cUTI

The secondary endpoints include:

- Number (and percentage) of patients in each arm with *microbiological eradication* of all baseline pathogens at the EOS visit; *microbiological eradication* of all baseline pathogens is defined as an end of study quantitative urine culture shows all uropathogens found at baseline are reduced to <10⁵ CFU/mL and all baseline pathogens are not detected by EOS urine PCR (Cq>33)
- Subjective measurement of Treating Investigator Satisfaction Score as evaluated by the questionnaire at EOS
- Turnaround Time (TAT: as measured in hours) of molecular diagnostic procedures compared to conventional diagnostics (time from collection of samples to complete identification of organism(s) and availability of antibiotic sensitivity results)
- Overall agreeability between the diagnostic results generated by PCR versus C&S as assessed by discordant analysis

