	study baseline urine is obtained
	E6. Pregnant women with known fetal congenital anomaly (e.g.,
	genetic abnormality or major congenital malformation)
	based on antenatal ultrasound;
	E7. Any rapidly progressing disease or immediately life-
	threatening illness, including acute hepatic failure, or
	respiratory failure
	E8. Medical condition or other factor that in the judgment of the
	investigator might affect ability to comply with procedures.
Study Duration	The duration of study participation for each enrolled patient is
	approximately 28 days.
Study Endpoints	Primary Endpoint:
	Number (and percentage) of patients in each study arm with
	favorable clinical outcomes* at the EOS visit
	*favorable clinical outcomes are defined as a clinical response of
	improvement ^a and/or cure ^b
	^a Clinical improvement is defined as 1) Resolution of cUTI signs
	and symptoms present at baseline, 2) Development of no new cUTI
	symptoms and/or 3) Avoidance of parenteral antibiotic therapy, in
	or out of hospital, at any time after randomization
	^b Clinical cure is resolution of all acute signs and symptoms of
	cUTI and improvement to such an extent that no further

Effective Date: 06/23/2023 Page **10** of **44**

	antimicrobial therapy (IV or oral) is required for the treatment of the cUTI
	Secondary Endpoints:
	 Number (and percentage) of patients in each arm with microbiological eradication** of all baseline pathogens at the EOS visit **microbiological eradication of all baseline pathogens is defined as an end of study quantitative urine culture that shows all uropathogens found at baseline are reduced to <10⁵ CFU/mL and all baseline pathogens are not detected by EOS urine PCR (Cq>33) Subjective measurement of Treating Investigator Satisfaction Score as evaluated by the questionnaire at EOS Turnaround Time (as measured in hours) of molecular diagnostic procedures compared to conventional diagnostics (time from collection of samples to complete identification of organism(s) and availability of antimicrobial susceptibility results)
	Overall agreeability between the diagnostic results generated by PCR versus C&S as assessed by discordant analysis
	 Safety: Assessments of safety will include the following: Clinical observations Vital sign measurements Laboratory tests Reported adverse events Assessment of Treatment Emergent Adverse Events (TEAE) at EOS

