4. STUDY OBJECTIVES AND ENDPOINTS

This investigation intends to verify the clinical utility of urine PCR testing by comparing the diagnostic and therapeutic values of molecular diagnostic methods to traditional urine C&S in management of cUTI in adults.

Table 2. Study Objectives and Endpoints

OBJECTIVES	ENDPOINTS		
Primary			
To evaluate patients' symptomatic responses following diagnosis and treatment based on the results of the molecular methods versus the those of conventional urine culture method	• Number (and percentage) of patients in each study arm with favorable clinical outcome* at the EOS visit *favorable clinical outcomes are defined as a clinical response of improvement and/or cure a Clinical improvement is defined as 1) Resolution of cUTI signs and symptoms present at baseline, 2) Development of no new cUTI symptoms and/or 3) Avoidance of parenteral antibiotic therapy, in or out of hospital, at any time after randomization b Clinical cure is resolution of all acute signs and symptoms of cUTI and improvement to such an extent that no further antimicrobial therapy (IV or oral) is required for the treatment of the cUTI		

UPH-STD-05-01 Version: 0

Effective Date: 06/23/2023 Page **14** of **44**

Advarra IRB Approved Version 0, Date: 12 May 2023 / Pro00071764

Secondary

- To determine the efficacy of antibiotic selection using molecular methods versus the conventional urine culture method
- To assess clinical utility of PCR results during the clinical-decision-making phase in patient care
- To compare the availability of the antimicrobial susceptibility information from molecular testing and conventional testing at the time of initial antimicrobial therapy
- To quantify the overall agreeability between the diagnostic results generated by PCR versus C&S

- Number (and percentage) of patients in each arm with microbiological eradication** of all baseline pathogens at the EOS visit
 - **microbiological eradication of all baseline pathogens is defined as an end of study quantitative urine culture that shows all uropathogens found at baseline are reduced to <10⁵ CFU/mL and all baseline pathogens are not detected by EOS urine PCR (Cq>33)
- Subjective measurement of Treating Investigator
 Satisfaction Score as evaluated by the questionnaire at EOS

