5. STUDY DESIGN

5.1. General Design

This is a multi-center, randomized, parallel-assignment, open-label, clinical utility study to evaluate urine PCR cUTI testing by comparing the diagnostic and therapeutic outcomes of molecular diagnostic methods to those of traditional urine C&S in management of cUTI in adults. At least six (6) sites will participate in this study. Approximately 120 eligible volunteers will be enrolled per site. The study is designed to be a 28-day study, which includes sample collection, sample test, treatment, and follow-up. Patients who meet all of the inclusion criteria and none of the exclusion criteria and sign an informed consent form will be enrolled in the study. During the visit, each enrolled patient will provide a urine sample (at least 8 mL) at V1 and V3; The collected urine specimens will be analyzed using both PCR and C&S methods at

UPH-STD-05-01 Version: 0

[figure not shown]
Effective Date: 06/23/2023 Page **15** of **44**

each timepoint. Upon eligibility confirmation by treating Investigator(s), patients will be randomized in a 1:1 ratio as follows:

- Diagnosis and treatment based on the results of the urine PCR
- Diagnosis and treatment based on the results of the urine C&S

Table 1. Schedule of Assessments summarizes the study procedures to be performed at each study visit. Individual study procedures are described in detail below (see section 8). It may be required to perform outlined procedures at unscheduled time points, if deemed clinically necessary by the Investigator(s). Additional evaluation/testing may be deemed necessary by the Investigator(s) for reasons related to subject safety.

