8.3. Visit 2 - Treatment (Day 0 + 5)

Visit 2 MUST initiate within 24 hours of the test result (urine C&S or urine PCR as applicable to subject's assigned arm) becoming available and within specified buffer window. Study staff will record the data associated with the PCR test report or C&S test report in a dedicated eCRF, including time of the test reports.

Visit 2 may be conducted virtually, as per treating Investigator's discretion, if the patient care can be continued in an out-patient clinic/setting.

The identity of the patient will be confirmed by verbal verification of DOB and name. The Investigator or delegate will review medical history. Patients will be asked about any changes in their health, and any concomitant treatments administered since the last visit.

UPH-STD-05-01 Version: 0

Effective Date: 06/23/2023

Page 21 of 44

Doc Lab Inc. / Protocol Number 22-UPHUV-01 Advarra IRB Approved Version 0, Date: 12 May 2023 / Pro00071764

The treating Investigator will utilize the results of the patients' randomly assigned study arm for their clinical decision making and patient care. The treating Investigator MUST NOT* review the results of the (unassigned) comparator test before treatment.

*Exception: If the patient's assigned test detects no UTI, the treating Investigator will review the result of the comparator test. In the case of concordant result between two comparators (both negative), the patient will be referred to SOC and excluded from the study. In the case of discordant result, the patient will be referred to SOC and the result of patient care will be followed up by the Investigator or delegate. The patient data will be collected and used for discordant analysis as planned (refer to section 11.3.4).

The treating Investigator shall provide continuous patient care as per their medical decision(s). These include, but are not limited to: request of unscheduled visits, admission/referral of patient to receive in-patient care, administration of IV or oral antibiotics, in/out-patient care, or use of broad-spectrum antibiotics.

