11.3.3. Statistical Analysis of the Primary Endpoint

The primary endpoint (percentage of patients exhibiting *favorable clinical outcomes*) will be evaluated for both arms of the study. A one-tailed, independent proportions Fisher's exact-test_will be used to compare the PCR test procedure against the conventional (C&S) diagnostic procedure; the following hypotheses serve as the basis for the test:

$$H_0: p_{PCR}^{FCl} \le p_{C\&S}^{FCl}$$

 $H_1: p_{PCR}^{FCl} > p_{C\&S}^{FCl}$

where FCl indicates favorable clinical outcome (primary endpoint) as defined in the earlier sections of this protocol, PCR represents the test procedure and C&S represents the conventional procedure. A 95% confidence interval will be calculated with the test statistic. A p-value of less than 0.05 will trigger the rejection of the null hypothesis.

Prior to statistical testing, a test for normality will be performed to ensure that the primary endpoint data from both treatment arms have a normal distribution and similar sample

UPH-STD-05-01 Version: 0

Effective Date: 06/23/2023 Page **29** of **44**

variance. If either condition is violated, a non-parametric test will be performed in replacement of the t-test.

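### As worded in section 11.3.2, a patient whose baseline symptoms persist can be a primary-endpoint success, while section 8.4 and Appendix I call that patient a clinical failure, and nothing says which definition governs

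*Combined protocol and SAP*

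**What the plan says.** - **Section 11.3.2.** FCl is improvement and/or cure. The first improvement component is "Resolution of cUTI signs and symptoms present at baseline, and/or". The second, absence of new symptoms, ends with the same connector. The third is avoidance of parenteral antibiotics after randomization. For cure the section states: "Clinical cure is the resolution of all acute signs and symptoms of cUTI and improvement to such an extent that no further antimicrobial therapy" is needed.
- **Section 4, Table 2.** Here the components run "Resolution of cUTI signs and symptoms present at baseline, 2) Development of no new cUTI symptoms and/or 3) Avoidance of parenteral antibiotic therapy", with a comma after the first and a single connector before the third. The synopsis (section 2.1) has the same pattern: "symptoms and/or 3) Avoidance of parenteral antibiotic therapy, in".
- **Section 8.4.** A patient is a clinical failure with any one of three things at end of study (EOS): an AE or SAE still ongoing, cUTI symptoms that persist, or cUTI symptoms that are new.
- **Appendix I.** The questionnaire repeats that failure rule. Its improvement box accepts full resolution and also significant improvement short of it. It adds an Indeterminate box and has no box for cure.
- **Section 11.3.3.** The primary test is set up "where FCl indicates favorable clinical outcome (primary endpoint) as defined in the earlier sections of this protocol", without saying which section.
- **Section 11.1.** On the control rate: "we assumed an FCl percentage of 75% for the C&S arm". A 10% gain is said to need 574 participants; the G*Power inputs printed there are 0.7 and 0.8.

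**The concern.** The primary objective in section 4 is patients' symptomatic response. Under the rule in 11.3.2, a patient with no such response can be a success, and the same patient is a failure in the section that governs the EOS visit. Two analysts who each follow the protocol could code that patient differently in the only confirmatory test.

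At stake is what the comparison measures. Non-resolvers who qualify through another component are added to the successes in each arm, so the arm difference in FCl is no longer a difference in symptom response. One of those other components, parenteral therapy, is a treatment decision and not a symptom. Section 5.1 states: "This is a multi-center, randomized, parallel-assignment, open-label, clinical utility study". Section 8.3 leaves to the treating Investigator "admission/referral of patient to receive in-patient care, administration of IV or oral antibiotics, in/out-patient care, or use of broad-spectrum antibiotics".

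**Working it through.** **1. The plan's own figure.** Inputs from 11.1: one-sided Fisher exact test, alpha 0.05, 287 per arm, rates 0.70 and 0.80. Exact enumeration gives power 0.8513 (stated 0.8513193) and a test size at a common rate of 0.80 of 0.0404 (stated 0.0404397). So 2 × 287 = 574 reproduces. This confirms the arithmetic for that pair of rates. It does not show which endpoint they describe. The text of 11.1 gives 75%, and with 10 points added 85%; that mismatch with 0.70 and 0.80 is a separate matter, and both pairs are carried below.

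**2. Enumeration under 11.3.2.** Let R = baseline symptoms resolved, N = no new symptom, A = parenteral therapy avoided. FCl = R or N or A. Failure on symptoms under 8.4 = not R or not N.

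| R | N | A | FCl (11.3.2) | Failure on symptoms (8.4) |
|---|---|---|---|---|
| yes | yes | yes | yes | no |
| yes | yes | no | yes | no |
| yes | no | yes | yes | yes |
| yes | no | no | yes | yes |
| no | yes | yes | yes | yes |
| no | yes | no | yes | yes |
| no | no | yes | yes | yes |
| no | no | no | no | yes |

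Seven of 8 are FCl, and 5 of those 7 are also failures. Of the 4 combinations with R = no, 3 are FCl. Cure requires resolution, so it implies R and adds no combination. The counts weight all combinations equally and are not patient rates.

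**3. Readings open under the synopsis and Table 2.**

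| Reading | FCl, of 8 | Of these, failures on symptoms |
|---|---|---|
| R or N or A | 7 | 5 |
| (R and N) or A | 5 | 3 |
| R and (N or A) | 3 | 1 |
| R and N and A | 1 (2 with cure) | 0 |

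In the last row, cure is taken as R and N with no further antimicrobial needed.

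**4. Where A alone decides.** Under 11.3.2, A changes the result only when R and N are both no: 2 of 8 combinations. Under (R and N) or A, it decides whenever R and N are not both yes: 6 of 8.

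**5. Effect on the comparison.** Let r be an arm's resolution rate and q the share of its non-resolvers who meet N or A. Then

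FCl = r + (1 − r)q, which is at least r.

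The PCR minus C&S difference is (r_PCR − r_C&S) + [(1 − r_PCR)q_PCR − (1 − r_C&S)q_C&S]. The bracket is the part that is not resolution. The documents give no q for either arm.

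**6. What the rates in 11.1 would mean.** Under 11.3.2 a patient is not FCl only if R, N and A are all no. If all 287 per arm are assessed (an assumption), the share with all three is 1 − FCl:

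- Text rates: C&S 1 − 0.75 = 0.25, and 0.25 × 287 = 71.75, about 72 patients; PCR 1 − 0.85 = 0.15, and 0.15 × 287 = 43.05, about 43.
- G*Power rates: 1 − 0.70 = 0.30, and 0.30 × 287 = 86.1, about 86; 1 − 0.80 = 0.20, and 0.20 × 287 = 57.4, about 57.

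These would be patients with persistent symptoms, a new symptom and parenteral therapy together.

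**The case against.** The best defense is that nobody will apply the literal rule. Section 8.4 lists an assessment of clinical outcome at Visit 3 and leaves failure to the treating Investigator's determination. On the Appendix I form, unchanged symptoms would probably be entered as failure. That stands, and it lowers the practical risk. It does not settle the endpoint. No section derives FCl from the form, and among the endpoints in 11.3.2 the questionnaire is named only for the satisfaction score. The form's boxes also overlap: a patient with significant improvement and residual symptoms fits both improvement and failure. If the connectors were meant cumulatively, the text does not say so.

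Three stronger readings are tempting, and the documents do not support them.

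- *A reader might infer that open-label decisions on parenteral therapy drive the primary result.* Under 11.3.2, avoidance decides only for patients with both unresolved and new symptoms. The mechanism has more room under the (R and N) or A reading of the synopsis and Table 2. Neither its size nor its direction can be found from the documents.
- *A reader might infer a definite loss of power.* If 0.70 and 0.80 were resolution rates and the same q held in both arms, the difference would be (1 − q) × 10 points. For q = 0.25, 0.50 and 0.75 that is 7.5, 5 and 2.5 points, with power 0.71, 0.52 and 0.28 at 287 per arm. Both conditions are assumptions, so no power loss is claimed.
- *A reader might infer that the assumed rates are wrong because 25% and 15% look high for the triple combination.* The documents give no rate for that combination and do not show which endpoint the literature range describes. Those figures are only a reason to check.

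**Conclusion.** The point holds on the wording alone. Section 11.3.2 makes 7 of 8 component combinations favorable, 5 of those 7 contradict the failure rule in 8.4 and Appendix I, the synopsis and Table 2 admit several other rules, and 11.3.3 does not choose among them. FCl rates under the literal rule are the same as or higher than resolution rates, and the arm contrast no longer measures symptomatic response. The size of the distortion is not known, because it depends on the share of non-resolvers who qualify in each arm.

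The conflict also extends beyond symptoms. A fully resolved patient with any AE or SAE ongoing at EOS is FCl under 11.3.2 and a failure under 8.4. This should be corrected before any outcome is classified, because the primary endpoint cannot be computed uniquely as written.

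**What to change.** 1. Reconcile the synopsis, Table 2, 11.3.2, 8.4 and Appendix I into one definition with explicit AND/OR logic. A symptom response should be necessary for FCl; one example is R and N.
2. Make FCl and clinical failure mutually exclusive. The sponsor should state how each of these is classified: significant improvement short of resolution, avoidance of parenteral therapy (required, or reported separately), an ongoing AE or SAE in a resolved patient, and Indeterminate patients.
3. Derive FCl from explicit Visit 3 fields for baseline-symptom resolution and new symptoms, and name that derivation in 11.3.3. Concomitant medication is already recorded at that visit.
4. Confirm that the rates in 11.1 describe the reconciled endpoint. If they do not, recheck the 574.

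The cost is wording changes and a few eCRF fields, with no extra visit; section 16.3 has the forms built after the protocol is final. Reported FCl rates will be the same as or lower than under the literal rule. Whether the sample size changes depends on step 4.
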